12.4 Assessment of Safety

The safety population will be comprised of all subjects who receive at least one dose of study drug. Safety will be assessed by the NCI CTCAE V5. Please refer to the Study Calendar for the schedule of toxicity assessment.

Version Date: 18MAR2020 Confidential Page 33 of 41

12.5 Assessment of Efficacy

The efficacy evaluable population will be comprised of all subjects who receive at least one dose of study drug and either undergo at least one post-baseline assessment or die before any evaluation. Efficacy will be evaluated using RECIST 1.1 or MDA criteria (for subjects with bone only disease).

12.6 Data Analysis Plans

12.6.1 Analysis Plans for Primary Objective

In the efficacy evaluable population, in the chemo-sensitive group only the primary endpoint of PFS will be separately compared to the historical control rate of 3 months using a one-sided Sign Test for censored data (35). In both the chemo-sensitive and -resistant groups, PFS overall will be estimated with a Kaplan-Meier curve and median PFS with a 95% confidence interval.

12.6.2 Analysis Plans for Secondary Objectives

In the efficacy evaluable population, Objective Response and Disease Control Rate will be estimated with 95% confidence intervals. Overall survival (OS) will be estimated with a Kaplan-Meier curve and median OS with a 95% confidence interval. Toxicities will be tabulated in the Safety Population. All analyses will be separate for the chemo-sensitive and chemo-resistant groups.

12.6.3 Analysis Plans for Exploratory Objectives

Platinum induced DNA adducts in PBMCs and tumor tissue on Cycle 2 Day 5 will be analyzed. These will be compared to platinum induced DNA lesions isolated from PBMCs of a control group of patients that have completed standard of care treatment with 4 cycles of carboplatin (+ etoposide) enrolled under a separate protocol using two-sample t-tests. LINE1 methylation levels in PBMCs and baseline tumor biopsy for global DNA methylation status and selected genes, IHC expression of EZH2 will be described with box plots and means/standard deviations or median/quartiles, as appropriate, at each time point collected and with line plots over-time if appropriate. Paired t-tests or Wilcoxon signed-rank tests will be used to compare baseline measures to post-treatment measures (for LINE1 in PBMCs, IHC expression of EZH2).

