	This study is powered for chemotherapy sensitive patients. Chemotherapy resistant patients will be enrolled but analyzed separately and descriptively only. For the chemosensitive group, when the sample size is 24, a non-parametric test (single-group) with a one-sided 0.10 significance level will have 80% power to detect the difference between a median survival of 3.0 months vs 6.0 months. With 24 patients in the chemo-sensitive group, we expect to enroll approximate 34 subjects total, thus we will have approximately 10 chemo-resistant patients to generate pilot data from.
TOTAL NUMBER OF SUBJECTS	N = 34
ESTIMATED ENROLLMENT PERIOD	Estimated 18 months
ESTIMATED STUDY DURATION	Estimated 12 months

TABLE OF CONTENTS

Sch	ema	7
1.	Background and Rationale	8
2.	Study Objectives and Endpoints	
3.	Eligibility Criteria	
4.	Subject Registration	
5.	Treatment Plan	
6.	Toxicities and Dose Delays/Dose Modifications	
7.	Study Calendar & Evaluations	
8.	Biospecimen Studies and Procedures	
9.	Criteria for Disease Evaluation	
10	Drug Information	
11	Adverse Events	
12	Statistical Methods	
13	Trial Management	
14.	Data Handling and Record Keeping	
15	Ethics	
16	References	
- 0	110101 011000	••••••••••••

SCHEMA

- ES SCLC patients
- Must have prior treatment with platinum containing chemotherapy regimen
- PS 0-1
- Adequate organ function

Treatment Regimen

Guadecitabine 30mg/m² subcutaneously Days 1-5 Carboplatin AUC of 4 intravenously on Day 5 Continue for 4 cycles; 1 Cycle = 28 Days

Disease Assessment after completion of 4 cycles of treatment Continue follow up per protocol

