2.1.3 Correlative/Exploratory Objectives

- Measure platinum induced DNA adducts in peripheral blood mononuclear cells (PBMCs) and tumor tissue on Cycle 1 Day 1 and Cycle 2 Day 5 prior to carboplatin treatment.
- Methylation status change in PBMCs and tumor biopsy for global DNA and selected genes in tumor tissue on Cycle 1 Day 1 and Cycle 2 Day 5 prior to carboplatin treatment.
- Analyze IHC expression of EZH2 and EZH2 target genes on Cycle 1 Day 1, Cycle 2 Day 5 prior to carboplatin treatment and at progression (optional). EZH2 expression changes will be correlated with response to Guadecitabine in combination with carboplatin.
- Determine circulating tumor cell (CTC) burden prior to initiating treatment.

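### The DNA-adduct analysis tests tumour against control blood, compares PBMCs at unequal platinum exposure, and leaves the collected C1D1 baseline without a planned analysis

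*Combined protocol and SAP*

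**What the plan says.** The exploratory objectives (Section 2.1.3) call for adducts to be measured in PBMCs and "tumor tissue on Cycle 1 Day 1 and Cycle 2 Day 5 prior to carboplatin treatment". Section 8.1.2 requires biopsies at both times from 15 patients, with adducts among the purposes. Section 8.2.3 collects PBMCs at C1D1, C2D5 and progression and has platinum lesions quantified by ICP-MS.

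The analysis plan in Section 12.6.3 is narrower. It opens with "Platinum induced DNA adducts in PBMCs and tumor tissue on Cycle 2 Day 5 will be analyzed" and continues "These will be compared to platinum induced DNA lesions isolated from PBMCs of a control group of patients". Those patients had completed standard treatment "with 4 cycles of carboplatin (+ etoposide) enrolled under a separate protocol using two-sample t-tests". The paired baseline-to-post tests at the end of the section carry a restriction: "for LINE1 in PBMCs, IHC expression of EZH2". Adducts are not on that list.

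**The concern.** A two-sample test is useful when the groups would be expected to agree if the factor of interest had no effect. Here the study and control samples differ in several other ways, and for tumour they are not the same tissue. A difference could appear without any guadecitabine effect, or a real effect could be masked.

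Meanwhile the one comparison that removes each patient's own residual adducts is not planned. That matters because Section 3.1 requires prior first-line platinum of every patient, so the adduct level at C1D1 cannot be assumed to be zero. At stake is the mechanistic reading of a correlative for which some patients undergo a repeat biopsy.

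**Working it through.** The plan gives no sample size, effect size, SD or power for adducts, so there is no stated figure to reproduce.

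**1. Recent platinum exposure.** The Schema gives "Carboplatin AUC of 4 intravenously on Day 5" of each 28-day cycle. The C2D5 sample is drawn before that day's dose, so it follows one on-study dose (C1D5), nominally 28 days earlier. The comparator is a "control group of patients that have completed standard of care treatment with 4 cycles of carboplatin". The count is 1 against 4.

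**2. The two groups side by side.**

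| Feature | Study, C2D5 | External controls |
|---|---|---|
| Tissue | PBMC and tumour | PBMC only |
| Recent carboplatin cycles | 1 | 4 |
| Etoposide in the regimen | No | Given as (+ etoposide) |
| Guadecitabine | Yes | Not mentioned |
| Time since last platinum | About 28 days | Not stated |
| Prior platinum | First-line, all patients | Not stated |
| Carboplatin dose, group size | AUC 4; up to 34 | Not stated |

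**3. Can the direction of the PBMC bias be fixed?** The following model is illustrative, and its assumptions are not in the documents: equal doses every 28 days in both groups, a share r of adducts kept over 28 days, no residual from earlier platinum, and guadecitabine multiplying adducts by g.

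- Study level at C2D5: g × r.
- Control level 28 days after dose 4: r + r² + r³ + r⁴. The groups tie at g = 1 + r + r² + r³.
- Control level just after dose 4: 1 + r + r² + r³. They tie at g = (1 + r + r² + r³)/r.
- Control level three cycles after dose 4: r² × (r + r² + r³ + r⁴). They tie at g = r² × (1 + r + r² + r³).

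| r | Just after dose 4 | One cycle after | Three cycles after |
|---|---|---|---|
| 0.1 | 11.11 | 1.11 | 0.01 |
| 0.25 | 5.31 | 1.33 | 0.08 |
| 0.5 | 3.75 | 1.88 | 0.47 |
| 0.75 | 3.65 | 2.73 | 1.54 |
| 1.0 | 4.00 | 4.00 | 4.00 |

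Worked case, r = 0.5: 1 + 0.5 + 0.25 + 0.125 = 1.875, and 0.25 × 1.875 = 0.47. A value above 1 means guadecitabine must raise adducts by that factor merely to match controls. A value below 1 means study patients exceed controls with no guadecitabine effect. Both occur, so the sign cannot be settled without the control sampling time.

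**4. What a paired analysis could detect.** For a paired t-test, two-sided 5%, 80% power, the detectable mean change d, in SDs of the within-patient differences, solves the noncentral t power equation with n − 1 degrees of freedom and noncentrality d√n.

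| Complete pairs | Exact t | Normal approximation, (1.960 + 0.842)/√n |
|---|---|---|
| 34 (all patients, PBMC) | 0.495 | 0.48 |
| 24 (chemo-sensitive, PBMC) | 0.597 | 0.57 |
| 15 (biopsies) | 0.778 | 0.72 |

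These figures describe the replacement analysis, not the size of the present bias. They are best-case: footnote 5 of the Study Calendar requires the repeat biopsy only where feasible, patients may stop before C2D5, and 34 pools the sensitive and resistant groups, which the protocol otherwise analyses separately.

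**The case against.** The strongest reply is that the paired change does not isolate guadecitabine either. C1D1 precedes all study treatment, while C2D5 follows guadecitabine and one carboplatin dose, so carboplatin alone could raise adducts between the two. The external group is also the only comparison with carboplatin given without guadecitabine. Both points stand. They are reasons to label the paired result correctly and to keep the PBMC comparison as supportive; they do not rescue the tumour-against-blood test or explain the unused baseline.

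Three stronger readings are tempting, and the documents do not support them.

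- A reader might infer that the comparison can say nothing about guadecitabine. Section 12.6.3 does not state that as its aim; the aim is inferred from the preclinical ICP-MS finding in Section 1.4. If sampling times prove comparable, PBMC against PBMC could be partly informative.
- A reader might infer that study patients have had less platinum overall. The 1 against 4 counts on-study cycles only. All had first-line platinum, and the controls' history is not given.
- A reader might infer that tumour methylation change also needs a formal test. Section 12.6.3 provides summaries by time point and plots over time, which can serve an exploratory objective. A p-value there is a preference.

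It may also be said that *these* in Section 12.6.3 was meant to cover PBMCs only. In that case tumour adducts have no comparison at all, and the wording still needs correcting. The allowance in Section 12 for further exploratory analyses is too general to count as a planned C1D1 analysis.

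**Conclusion.** The point holds in a limited form, and its severity is minor. Read literally, the plan produces a tumour-against-blood p-value with no usable meaning. Its PBMC comparison is confounded by recent carboplatin cycles, etoposide and source protocol, and possibly by time since last platinum and platinum history. The direction of that bias is unknown, and its size cannot be given from the documents: the tie factors run from 0.01 to 11.11 under assumed retention and sampling times. The C1D1 adduct data have no stated use.

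This rests on the literal reading of Section 12.6.3 and on the schedule being followed as planned. The PFS test, the 24-patient sample size and the safety analysis are unaffected.

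**What to change.** In Section 12.6.3:

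1. Add platinum-DNA adducts to the measures covered by the paired t-test or Wilcoxon signed-rank test, so that the within-patient C1D1 to C2D5 change is analysed separately for PBMCs and for tumour.
2. State that this change reflects guadecitabine plus carboplatin jointly and does not isolate guadecitabine.
3. Drop the t-test of study tumour against control PBMCs.
4. Keep the external comparison for PBMC against PBMC, labelled supportive and non-confirmatory, and report the number of carboplatin cycles and days since last platinum in both groups.
5. Report the number of complete pairs for each tissue, and say whether the sensitive and resistant groups are pooled.

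The cost is a few sentences and two more paired analyses. No new samples or visits are needed, since both time points are already scheduled. The control records must yield cycle counts and dates of last platinum. The external comparison loses its inferential standing, which is a small loss given the confounding.

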12.6.4 Other Planned Analyses

For the enrolled population (all subjects who are enrolled onto the trial), descriptive statistics will be used to characterize subject demographic and clinical characteristics, disposition, and significant protocol violations. In the safety population, concomitant medications and exposure will be described.

Version Date: 18MAR2020 Confidential Page 34 of 41

13 TRIAL MANAGEMENT

13.1 Data and Safety Monitoring Plan (DSMP)

The study will be conducted in accordance with the Indiana University Melvin and Bren Simon Cancer Center's (IUSCC) DSMP for High Risk Safety Lead-In/Phase II Trials.

HCRN oversight activities include:

- Review and processing of all adverse events requiring expedited reporting as defined in the protocol
- Provide trial accrual progress, safety information and data summary reports to the sponsor-investigator, including a weekly update of aggregate AE data.
- Investigators will conduct continuous review of data and patient safety. For any increase in frequency of grade 3 or above adverse events (above the rate reported in the Investigator Brochure or package insert), the sponsor investigator will notify HCRN who will notify the DSMC Chair immediately. The notification will include the incidence of study adverse events, grades, and attributions, as well as investigator statements regarding comparison with risks per the IB/ package insert.
- Notify participating sites of adverse events potentially requiring expedited reporting and subsequent DSMC recommendations for study modifications.
- Investigators will conduct continuous review of data and patient safety.
- Coordinate monthly meetings which will include representation from each accruing site.
 - These meetings should include review of data, the number of subjects and significant toxicities as described in the protocol. HCRN should maintain meeting minutes and attendance for submission to the DSMC upon request.
- Conduct the trial across all participating sites in accordance with the requirements set forth in the IUSCC DSMP.

13.2 Indiana University Melvin and Bren Simon Cancer Center's Data Safety Monitoring Committee

The IUSCC Data and Safety Monitoring Committee (DSMC) is responsible for oversight of subject safety, regulatory compliance, and data integrity for this trial. The DSMC will review this study to assess toxicity, compliance, data integrity, and accrual per the Institutional DSMP. Trials managed by HCRN are not routinely audited or monitored by IUSCC; however, the IUSCC DSMC retains the right to audit HCRN trials on a for cause basis.

The IUSCC DSMC will review study data semi-annually during the active treatment and safety follow-up portion of the trial per the IUSCC DSMP.

In preparation for the IUSCC DSMC review, HCRN will provide the following:

- 1. Monthly Summary Reports
- 2. Reports of the following, if not already included in the Monthly Summary Report:
 - o Adverse event summary report (including serious adverse events)
 - Study accrual patterns
 - Protocol deviations
- Audit and/or monitoring results, if applicable
- Data related to stopping/decision rules described in study design

Version Date: 18MAR2020 Confidential Page 35 of 41

3. HCRN weekly (Phase I) or monthly (Phase II) study update meeting minutes/ attendance

Documentation of DSMC reviews will be provided to sponsor-investigator (SI) and HCRN. The IUSCC DSMC will notify the sponsor-investigator and other regulatory bodies, as appropriate, for issues of immediate concern. The sponsor-investigator will work with HCRN to address the DSMC's concerns as appropriate.

At any time during the conduct of the trial, if it is the opinion of the sponsor-investigator that the risks (or benefits) to the patient warrant early closure of the study, this recommendation should be made in writing to the DSMC Chair and Compliance Officer. Alternatively, the DSMC may initiate suspension or early closure of the study at any time based on its review of the study reports.

13.2.1 IND Annual Reports

For trials with an IND held locally by the IU principal investigator or university, the IND Annual Report will be prepared and submitted to the Compliance Team. This report will be reviewed by the DSMC at the time of FDA submission.

13.3 Data Quality Oversight Activities

Remote validation of the EDC system data will be completed on a continual basis throughout the life cycle of the study. Automated edit check listings will be used to generate queries in the EDC system and transmitted to the site to address in a timely fashion. Corrections will be made by the study site personnel.

13.3.1 Onsite Monitoring

Monitoring visits to the trial sites may be made periodically during the trial to ensure key aspects of the protocol are followed. Additional for cause visits may occur as necessary. Selected source documents will be reviewed for verification of agreement with data entered into the EDC system. It is important for the site investigator and their relevant personnel to be available for a sufficient amount of time during the monitoring visits or audit, if applicable. The site investigator and institution guarantee access to source documents by HCRN or its designee.

The trial site may also be subject to quality assurance audit by Astex Pharmaceuticals or its designee as well as inspection by appropriate regulatory agencies.

13.4 Compliance with Trial Registration and Results Posting Requirements

Under the terms of the Food and Drug Administration Modernization Act (FDAMA) and the Food and Drug Administration Amendments Act (FDAAA), the sponsor-investigator of the trial is solely responsible for determining whether the trial and its results are subject to the requirements for submission to the Clinical Trials Data Bank, http://www.clinicaltrials.gov. All results of primary and secondary objectives must be posted to CT.gov within a year of completion. The sponsor-investigator has delegated responsibility to HCRN for registering the trial and posting the results on clinicaltrials.gov. Information posted will allow subjects to identify potentially appropriate trials for their disease conditions and pursue participation by calling a central contact number for further information on appropriate trial locations and study site contact information.

Version Date: 18MAR2020 Confidential Page 36 of 41

14. DATA HANDLING AND RECORD KEEPING

14.1 Data Management

HCRN will serve as the Clinical Research Organization for this trial. Data will be collected through a web based clinical research platform (EDC system), a system compliant with Good Clinical Practices and Federal Rules and Regulations. HCRN personnel will coordinate and manage data for quality control assurance and integrity. Select data will be collected and entered into the EDC system by study site personnel from participating institutions.

14.2 Case Report Forms and Submission

Generally, clinical data will be electronically captured in the EDC system and correlative results will be captured in EDC system or other secure database(s). If procedures on the study calendar are performed for standard of care, at minimum, that data will be captured in the source document. Select standard of care data will also be captured in the EDC system, according to study-specific objectives.

The completed dataset is the sole property of the sponsor-investigator's institution and should not be exported to third parties, except for authorized representatives of appropriate Health/Regulatory Authorities, without permission from the sponsor-investigator and HCRN.

14.3 Record Retention

To enable evaluations and/or audits from Health Authorities/HCRN, the site investigator agrees to keep records, including the identity of all subjects (sufficient information to link records; e.g., hospital records), all original signed informed consent forms, copies of all source documents, and detailed records of drug disposition. All source documents are to remain in the subject's file and retained by the site investigator in compliance with the site contract with HCRN. No records will be destroyed until HCRN confirms destruction is permitted.

14.4 Confidentiality

There is a slight risk of loss of confidentiality of subject information. All records identifying the subjects will be kept confidential and, to the extent permitted by the applicable laws and/or regulations, will not be made publicly available. Information collected will be maintained on secure, password protected electronic systems. Paper files that contain personal information will be kept in locked and secure locations only accessible to the study site personnel.

Subjects will be informed in writing that some organizations including the sponsor-investigator and his/her research associates, HCRN, Astex Pharmaceuticals, IRB, or government agencies, like the FDA, may inspect their medical records to verify the information collected, and that all personal information made available for inspection will be handled in strictest confidence and in accordance with local data protection laws.

If the results of the study are published, the subject's identity will remain confidential.

Version Date: 18MAR2020 Confidential Page 37 of 41

15 ETHICS

15.1 Institutional Review Board (IRB) Approval

The final study protocol and the final version of the informed consent form must be approved in writing by an IRB. The site investigator must submit written approval by the IRB to HCRN before he or she can enroll subjects into the study.

The site investigator is responsible for informing the IRB of any amendment to the protocol in accordance with local requirements. In addition, the IRB must approve all advertising used to recruit subjects for the study. The protocol must be re-approved by the IRB, as local regulations require.

Progress reports and notifications of serious and unexpected adverse events will be provided to the IRB according to local regulations and guidelines.

15.2 Ethical Conduct of the Study

The study will be performed in accordance with ethical principles originating from the Declaration of Helsinki. Conduct of the study will be in compliance with ICH Good Clinical Practice, and with all applicable federal (including 21 CFR parts 56 & 50), state, or local laws.

15.3 Informed Consent Process

The site investigator will ensure the subject is given full and adequate oral and written information about the nature, purpose, possible risks and benefits of the study. Subjects must also be notified they are free to discontinue from the study at any time. The subject should be given the opportunity to ask questions and allowed time to consider the information provided.

The subject's signed and dated informed consent must be obtained before conducting any procedure specifically for the study. The site investigator must store the original, signed informed consent form. A copy of the signed informed consent form must be given to the subject.

Version Date: 18MAR2020 Confidential Page 38 of 41

